## 8.2 Treatments administered

In the MP (Cycle 1) subjects will be randomized to one of three treatment groups  
CCI

- In Group U, subjects will receive 20 U NT 201 in the GFL area, 20 U NT 201 in the HFL area, and 24 U NT 201 in the LCL area (12 U per side).
- In Group L, subjects will receive placebo in the GFL area, placebo in the HFL area, and 24 U NT 201 in the LCL area, 12 U per side.
- In Group P, all three areas will be treated with placebo.

In the OLEX period (Cycles 2 and 3), all subjects will receive NT 201 in all three areas  
CCI

Injections will be administered as described in Section 8.1.1.2.

CCI

In case of a public health emergency treatments may be halted or postponed.

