The study activities and visit schedules are shown in **CCI** for the MP and in **CCI** for the OLEX period. The clinical study protocol allows for a window of  $\pm 7$  days in scheduling of study visits for all post-baseline visits, except V3 where only a  $\pm 3$ -day window is allowed. The IP(s) must be injected by the investigator, who is trained and experienced in aesthetic BoNT treatment, at the study site. Following administration of IP(s), subjects will be observed for a minimum of 30 minutes at the site and will be asked by the investigator if any AEs have occurred since administration. Vital signs will be taken at the beginning of each study visit to ensure subject safety.

The last primary outcome visit will occur at Day  $30 \pm 7$  (V4) for each subject. For subjects not fulfilling the reinjection criteria, also not at the reassessment visit, the end-of-study visit will be performed directly and the subject will be discontinued from the study. For all other subjects, the end-of-study visit V17 will occur at Day  $120 \pm 7$  after last administration of the IP in Cycle 3. Unscheduled visits may be required in the case of AEs or premature discontinuation of the study. In this case, the final assessments as described for V17, will be performed as soon as possible. If additional safety follow-up is necessary after this visit, subjects may be contacted by telephone or be assessed in the clinic, depending on the nature of the follow-up required.

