#### **Safety Evaluation Set (SES)**

The SES is the subset of all subjects who were exposed to study medication at least once. Subjects in the SES analyses will be analyzed as treated.

Note: In the definition of the SES above, "as treated" relates to actual study treatment in MP.

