## 6 Statistical Analysis Methods

Continuous endpoints (values and changes from baseline/ cycle baseline, where applicable) will be summarized by number of subjects in the respective analysis set/ population (N), number of values analyzed (n), mean, standard deviation, median, quartiles, minimum, and maximum. If relevant, the number of values imputed due to missingness (nimp) will be reported for efficacy variables (see [Section 6.4.1](#)). Mean, quartiles, and median will be reported to one decimal place more than the data were collected, for the standard deviation two decimal places more will be displayed; for derived data, an adequate number of decimal places will be chosen.

For qualitative endpoints, absolute and percent frequencies (n, %) and, if applicable, shift tables will be displayed. Frequency tables will include the number of missing values, if applicable. Percentages will be calculated using the denominator of all subjects in a specified population or treatment group. The denominator will be specified in a footnote to the tables for clarification if not otherwise obvious. Percentages will be reported to one decimal place. In frequency tables based on observed cases, number of missing values will not be presented and percentages will be based on number of observed cases (Nobs).

If not otherwise specified, statistical tests will be conducted two-sided at type I error rate 5%. P-values will be reported to four decimal places (e.g., p=0.0375). P-values below 0.0001 will be presented as '<0.0001'. Confidence intervals (CIs) will be two-sided 95%.

In general, values obtained at Visit 2 are defined as the baseline values. Where data is not recorded at Visit 2, the last measurement before start of treatment is defined as baseline value. These values will be analyzed as baseline (i.e. baseline flag is 'yes' for last record with non-missing value before first treatment in Study Data Tabulation Model [SDTM]). For cycle 2 values obtained at Visit 8 and for cycle 3 values obtained at Visit 13 will be used as cycle baselines.

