## 6.2 Safety Endpoints

All safety analyses will be performed on the SES. All safety tables will be presented by actual treatment group (“Group P”, “Group U”, “Group L”) at V2 in MP. In TEAE tables for total OLEX period, Cycle 2, and Cycle 3, the column headers for these three treatment groups will be “MP Group P”, “MP Group U”, “MP Group L”. TEAE tables for MP will additionally include a “Total NT 201” column for which active treatment groups (Group U and Group L) will be pooled. TEAE tables for total OLEX period, Cycle 2, and Cycle 3 will present pooled results from all three treatment groups in the fourth column, which will

be labeled "Total". For TEAE analyses over total study period, the columns "MP Group P - MP", "MP Group P - OLEX", "MP Group U", "MP Group L" and "MP Total NT 201" ("MP Group P - OLEX, MP", "Group U" and "Group L" pooled) will be presented. In column "MP Group P - MP" only AEs which occurred during MP are counted, in column "MP Group P - OLEX" only AEs which occurred in OLEX period are counted.

All analyses of laboratory values from any timepoint (Screening V1 and end-of-study visit V17) will be performed by actual treatment group at V2 in MP and in total. All analyses of vital signs from any timepoint will be performed by actual treatment group at V2 in MP, Total NT 201 (labeled "MP Total NT 201" for analysis of vital signs from visits total OLEX period) and in total.

AEs will be coded according to the MedDRA version in effect at the time the database is closed. Only TEAEs will be analyzed, which are defined as AEs with onset or worsening on or after date of the first administration of investigational product (IP) up to and including end of study visit (V17). In case no end of study visit (V17) is performed, all AEs reported during a time period corresponding to the expected cycle length will be regarded as treatment-emergent. Further details for separation of TEAEs and non-TEAEs can be found in **CCI** Non-TEAEs will be listed only.

All analyses of TEAEs will be based on the following time periods:

- Total study period
- MP (Cycle 1)
- Total OLEX period (Cycle 2 and Cycle 3)
- Cycle 2
- Cycle 3.

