TEAEs of the MP are defined as AEs with onset or worsening on or after date and time of the first administration of IP at V2 and before date and time of administration of IP in V8 (Cycle 2) or up to and including end of study visit (V17) in case of premature discontinuations prior to V8. For subjects who do not receive study treatment during OLEX period all AEs with onset or worsening on or after date and time of the first administration of IP up to and including end of study visit (V17) will be considered as TEAEs of MP. In case no end of study visit (V17) is performed, all AEs with onset or worsening up to and including Day 120 of MP will be regarded as TEAEs of MP.

TEAEs of the total OLEX period are defined as AEs with onset or worsening on or after date and time of the first administration of IP during OLEX period at V8 and up to and including end of study visit (V17). In case no end of study visit (V17) is performed, all AEs with onset or worsening at or after date and time of the first administration of IP during OLEX period at V8 and up to and including Day 120 of last cycle will be regarded as TEAEs of OLEX. TEAEs of Cycle 2 are defined as AEs with onset or worsening on or after date and time of the first administration of IP at V8 and before date and time of administration of IP at V13 (Cycle 3) or up to and including end of study visit (V17) in case of premature discontinuations prior to V13 or in case no study treatment is administered at V13. In case no end of study visit (V17) is performed, all AEs with onset or worsening at or after date and time of the first administration of IP at V8 and up to and including Day 120 of Cycle 2 will be regarded as TEAEs of Cycle 2. TEAEs of Cycle 3 are defined as AEs with onset or worsening on or after date and time of the first administration of IP at V13 and up to and including end of study visit (V17). In case no end of study visit (V17) is performed, all AEs with onset or worsening at or after date and time of the first

administration of IP at V13 and up to and including Day 120 of Cycle 3 will be regarded as TEAEs of Cycle 3.

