For analysis over the total study period, the number of subjects in the SES will serve as the denominator for calculation of incidences. For the analyses by treatment cycle the denominator will be adjusted to all subjects being treated in that treatment cycle. For the analysis over the total OLEX period, the denominator for the incidences will be all subjects being treated at least once in total OLEX period.

If an AE worsens between start and end of this AE it will be considered as new AE starting with the date of worsening. In this case the imputation of end dates within episodes of the same AE will be done by setting the end date/end time to start date/start time of the consecutive worsening record.

For analysis, incompletely recorded or completely missing start of AEs will be estimated according rules laid down in **cci** [REDACTED] End dates will not be imputed. In the AE listing, start date as recorded and as imputed for analysis will be displayed.

Calculation of time to onset/duration of AEs (days):

- Time to onset of an AE is defined as start date of AE - date of first administration of study drug in respective treatment cycle [+ 1 day for TEAEs]
- The duration of an AE will be calculated as stop date - onset date + 1 day.

If a subject has more than one intensity/ causal relationship to treatment/ outcome within a preferred term (PT) only the worst intensity/ causal relationship to treatment/ outcome will be considered for calculation of incidence rates in the frequency tables reporting incidences by intensity/ causal relationship to treatment/ outcome. Incidence of TEAEs related to COVID-19 disease and TEAEs related to COVID-19 vaccination will only be calculated overall. Thereby, TEAEs with missing relationship will be ignored but affected subjects will not be removed from the denominator. Also, for the analysis overall, i.e. for subjects with at least one TEAE, only the worst intensity/ causal relationship to treatment/ outcome category per subject will be counted for calculating incidence rates. The same applies to calculation of overall incidence of TEAEs related to COVID-19 disease and TEAEs related to COVID-19 vaccination.

[figure not shown]
The worst outcome is defined in the following order (worst outcome to best outcome):

- fatal
- unknown
- not recovered/not resolved
- recovering/resolving
- recovered/resolved with sequelae
- recovered/resolved

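### In the total-study TEAE table, the SES denominator puts placebo-only subjects into two NT 201 columns and lowers their incidences

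*SAP*

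**What the plan says.** SAP 6.2 (Safety Endpoints) defines separate TEAE analyses for the total study period, the MP, the total OLEX period and each OLEX cycle.

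- **Columns.** The total-study table splits Group P into *MP Group P - MP* and *MP Group P - OLEX*. In the second, "only AEs which occurred in OLEX period are counted". That column is then pooled with Groups U and L to form *MP Total NT 201*.
- **Total-study denominator.** "For analysis over the total study period, the number of subjects in the SES will serve as the denominator for calculation of incidences".
- **Total-OLEX denominator.** For that separate analysis, "the denominator for the incidences will be all subjects being treated at least once in total OLEX period". By-cycle tables use the subjects treated in the cycle.
- **SES membership (SAP 4).** "The SES is the subset of all subjects who were exposed to study medication at least once". Subjects are grouped by their actual MP treatment.
- **General rule for percentages (SAP 6).** "Percentages will be calculated using the denominator of all subjects in a specified population or treatment group". The denominator is to be footnoted where it is not otherwise obvious.
- **Group P in the MP (Protocol 8.2).** "In Group P, all three areas will be treated with placebo".
- **Subjects who fail the reinjection criteria, also at reassessment (Protocol 9.2).** "the end-of-study visit will be performed directly and the subject will be discontinued from the study".
- **Their events (SAP 6.2).** "For subjects who do not receive study treatment during OLEX period all AEs with onset or worsening" from first dose up to the end-of-study visit count as TEAEs of the MP.

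**The concern.** The numerators of the two columns are sorted by exposure to NT 201, but the denominators are not. A Group P subject who receives placebo in the MP and nothing afterwards is in the SES under Group P. All of that subject's events belong to the MP, so none can appear under *MP Group P - OLEX* or reach *MP Total NT 201*. The subject still counts in both denominators. The error has one direction: it can only lower the reported incidence on NT 201.

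The plan expects such subjects, because it allows for non-completion of the MP and discontinues those who do not meet the reinjection criteria.

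Two things are at stake. *MP Total NT 201* is the column a reader would take as the whole-study NT 201 experience, and under SAP 6.2.2 the same columns are used for related TEAEs. In addition, the same former-placebo OLEX events will be reported with two different incidences in one study report, because the total-OLEX table has its own, exposure-based denominator.

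**Working it through.** **Inputs**

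- Planned group sizes: U 180, L 90, P 90 (SAP 3). Assume all 360 are dosed, so the SES is 360.
- Let *d* be the share of Group P never injected in OLEX. The documents give no value. SAP 3 allows about 15% non-completion of the MP overall, and this is borrowed as the base case. It is the allowance behind the plan's statement of more than 150 Group U completers: 180 × 0.85 = 153, which reproduces.
- The documents give no TEAE incidence, so a true incidence of 10.0% is used for illustration.
- The SES denominator is read per column, as the SES subjects of that group, following the general rule in SAP 6.

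**Formulas**

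- *MP Group P - OLEX*: subjects exposed to NT 201 = 90 × (1 − d). Denominator as written = 90. Reported/true = 1 − d, so the relative understatement is d.
- *MP Total NT 201*: subjects exposed to NT 201 = 180 + 90 + 90 × (1 − d) = 360 − 90d. Denominator as written = 360. Reported/true = 1 − 90d/360 = 1 − d/4, so the relative understatement is d/4.

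**Results**

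| d | Group P exposed in OLEX (against 90) | Understatement | True 10.0% shows as | Pooled exposed (against 360) | Understatement | True 10.0% shows as |
|---|---|---|---|---|---|---|
| 5% | 85.5 | 5% | 9.5% | 355.5 | 1.25% | 9.9% |
| 15% | 76.5 | 15% | 8.5% | 346.5 | 3.75% | 9.6% |
| 30% | 63 | 30% | 7.0% | 333 | 7.5% | 9.25% |

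**Illustration in whole subjects.** Suppose 14 of the 90 are not reinjected and 8 of the other 76 have an OLEX TEAE. The Group P column of the total-OLEX table shows 8/76 = 10.5%. The *MP Group P - OLEX* column of the total-study table shows 8/90 = 8.9%. The pooled column divides by 360 instead of 346, a relative understatement of 14/360 = 3.9%.

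**Columns not affected.** *MP Group P - MP* counts MP events in subjects dosed with placebo in the MP. *MP Group U* and *MP Group L* contain only subjects dosed with NT 201 in the MP. In all three, the SES subjects of the group are the right denominator.

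**The case against.** The strongest reply is that the SAP sentence is loose rather than wrong. Taken literally it could mean the whole SES for every column, which nobody would program, so some column-level reading has to be supplied. A programmer could then apply the total-OLEX denominator to a column that counts only OLEX events and carry that number into the pooled column. The mock tables that serve as output specifications are not visible and may do this. However, SAP 6.2 lists the total-study and total-OLEX periods as separate analyses, each with its own stated denominator, and no readable text extends the OLEX rule to these columns. The per-group reading used here is also the one more favourable to the plan. The whole SES would dilute *MP Group P - OLEX* further.

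The size is open to challenge, and that stands in part. The 15% is a general allowance. SAP 3 also words it as up to 15% not completing the study, which would make the loss before OLEX smaller. Placebo subjects are the least likely to be held back from reinjection by a persisting effect. The upper end of the range has no source in the documents. For these reasons *d* is given as an assumption with a range. The direction of the error does not depend on it.

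It is also true that the consequence is limited. No test or endpoint uses either column, event counts do not change, and the total-OLEX table gives the former-placebo incidence on a proper denominator. A denominator footnote would explain why the two percentages differ, but it would leave placebo-only subjects in columns presented as NT 201 experience.

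**Conclusion.** The concern holds. If the stated rule is followed, *MP Group P - OLEX* and *MP Total NT 201* understate TEAE incidence on NT 201 whenever at least one dosed Group P subject is not reinjected and the true incidence is above zero. *MP Group P - OLEX* will then also contradict the total-OLEX table. The relative understatement equals the share of Group P not reinjected in the first column and a quarter of that share in the pooled column. That is material for the first and small for the second at the borrowed 15%. These figures assume that all 360 planned subjects are in the SES and that the SES count is taken per treatment group. If every dosed Group P subject were reinjected, the error would be zero.

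The scope is two columns of a descriptive table family. The efficacy analyses, the MP, total-OLEX and by-cycle safety tables, and the secondary safety endpoints are not touched. The point should be corrected, but it does not threaten the trial's main conclusions.

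**What to change.** In SAP 6.2, replace the single total-study denominator with one set by column:

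- *MP Group P - OLEX*: Group P subjects treated at least once in OLEX.
- *MP Total NT 201*: all subjects who received NT 201 at least once.
- *MP Group P - MP*, *MP Group U*, *MP Group L*: SES subjects of that group.

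Optionally, add a footnote that the columns cover different numbers of treatment cycles and that the comparison of active treatment with placebo should be read from the MP table.

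The cost is a short SAP wording change and reprogramming of one table family, with no new data. The percentages in the two NT 201 columns rise slightly, and the former-placebo OLEX incidence then agrees with the total-OLEX table.

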Data pertaining to AEs will be collected during each study visit on the basis of the subject's spontaneous report, through investigator inquiry, or discovered in the course of examinations performed during the visit. The investigator will assess and record any AE in detail in the source documentation and on the eCRF AE report form. The following information must be recorded:

- AE diagnosis or main symptom.
- Date of onset.
- Date of worsening (e.g. if an AE turns from mild to moderate, the date has to be given).
- Intensity (see [Section 10.1.1](#)).
- Causal relationship (not related, related).
- Causal relationship to COVID-19 (not related, related)
- Serious (yes or no).
- Outcome ([Section 10.1.4](#)).
- AE leading to discontinuation of the study (yes or no).
- Stop date.

After completion of all scheduled visit assessments, the investigator must document any AEs arising from these assessments.

In case of an SAE or AESI (alert term, as defined in [Section 10.3](#)) the investigator must also complete an SAE report form or AESI report form and report it to the CRO immediately, as described in [Section 10.2](#).

Treatment of overdose with IP(s) is described in [Section 8.2.6](#).

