AEs coded as “Immunisation reaction” (preferred term) are defined as AEs related to COVID-19 vaccination.

The AEs listed in **cci** [REDACTED] are defined as adverse event of special interest (AESIs) for this study.

CCI

In case of missing intensity or missing causal relationship of an AE to treatment, the worst case principle will be applied, i.e., a missing intensity will be set to “severe” and a missing causal relationship will be set to “related”. Missing outcome will be set to “unknown”. Missing causal relationship to COVID-19 disease will not be imputed. TEAEs with missing relationship to COVID-19 disease will be ignored for calculation of the respective incidence rates but affected subjects will be kept in the denominator and only TEAEs which are documented as related to COVID-19 disease will be included in respective listing. No missingness is expected for relationship of TEAEs to COVID-19 vaccination.

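### The incidence of COVID-19-vaccination-related AEs rests on one MedDRA term that names no vaccine, so it can include reactions to other vaccines and can miss COVID-19 vaccine reactions coded as symptoms

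*SAP*

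**What the plan says.** SAP 6.2 takes AEs coded as *Immunisation reaction* and states: "preferred term) are defined as AEs related to COVID-19 vaccination". The rule sets no condition on the vaccine product, the date of vaccination or the investigator's judgement. Three other statements in SAP 6.2 bear on it:

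- The output it feeds: "Incidence of TEAEs related to COVID-19 disease and TEAEs related to COVID-19 vaccination will only be calculated overall".
- Completeness: "No missingness is expected for relationship of TEAEs to COVID-19 vaccination".
- Coding: "AEs will be coded according to the MedDRA version in effect at the time the database is closed".

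For COVID-19 disease, SAP 6.2 works from recorded causality instead: "only TEAEs which are documented as related to COVID-19 disease will be included in respective listing". Missing values of that item are acknowledged and left unimputed.

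On the data side, the AE item list in Protocol 10.1 has the investigator enter "AE diagnosis or main symptom". It also has one pandemic causality item, "Causal relationship to COVID-19 (not related, related". The list contains no item for vaccination.

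**The concern.** The table label speaks of a relationship to COVID-19 vaccination, but what is counted is a coded term that by its name covers immunisation in general. The two can differ in either direction. A reaction to another vaccine that is coded to this term is counted. A COVID-19 vaccine reaction entered as fever or headache, and coded to that symptom, is not counted, even if the verbatim term names the vaccine.

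The matter is not idle in this study. The planned period runs from Q4 2020 to Q3 2022 (Protocol synopsis), each subject is followed for about 360 days plus screening and any reassessment time, and the SAP was written against a protocol version dated 24 June 2021. At stake is whether a reader of the study report can take this one incidence at face value.

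**Working it through.** The documents state no expected figure for this incidence, so there is nothing to reproduce. The check sets the rule beside the data that feed it.

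**1. What enters the count.** Under SAP 6.2, a TEAE counts if and only if its preferred term is *Immunisation reaction*. The 'only if' is an inference: the SAP does not write 'only'. It does give a definition, no alternative criterion can be read, and the expectation of no missing values fits a flag derived from the code alone, which always returns yes or no.

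**2. Can a reaction to another vaccine enter?** Yes. The term names no product. The readable part of the prohibited-medication list in Protocol 8.3 does not bar other vaccines (parts of that section are redacted).

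**3. Can a COVID-19 vaccine reaction stay out?** Yes. Protocol 10.1 accepts a main symptom in place of a diagnosis. No readable convention sends post-vaccination symptoms to *Immunisation reaction*.

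**4. Is there a recorded item to correct the flag?** Not in the list in Protocol 10.1. Its pandemic causality item names COVID-19, and SAP 6.2 uses a COVID-19 disease relationship for the separate disease category.

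**5. Net effect.** Define, for any analysis period:

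- T = subjects with at least one TEAE truly related to a COVID-19 vaccine;
- m = subjects within T who have no TEAE coded *Immunisation reaction*;
- f = subjects outside T who have at least one TEAE coded *Immunisation reaction*;
- N = the denominator. For the total study period, "the number of subjects in the SES will serve as the denominator for calculation of incidences"; by cycle, it is the subjects treated in that cycle.

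Reported incidence = (T − m + f) / N. True incidence = T / N. Error = (f − m) / N.

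The documents give no value or range for T, m or f. The error can be positive, negative or zero, and a zero would still hide misclassified subjects if f and m were equal and above zero.

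**6. Where the flag is used.** The readable text uses it for this incidence only. It removes no TEAE and does not alter the relationship to NT 201, which is a separate AE item (Protocol 10.1), defined against the investigational product (Protocol 10.1.2) and set to related when missing (SAP 6.2). AESIs are asked about at every visit from V2 and reported whether or not considered related (Protocol 10.3). The secondary safety endpoints count related TEAEs in the main and open-label periods (SAP 5.2.2) and do not use the flag.

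**The case against.** The strongest reply is that this is a labelling weakness in a descriptive table, and that misclassification depends on material that cannot be seen. Sites may have entered vaccine reactions as a diagnosis, coders may have followed a convention that maps them to this term, and few other vaccines may have been given. Parts of SAP 6.2 are redacted, and the data validation plan and Data Management Plan cited in Protocol 11.3 are not available. This stands as a limit: the rule *can* include and *can* miss, and it is not shown that it does. It does not rescue the definition as it reads. If a convention exists, the definition should cite it.

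It is also fair to say that the sentence on missing values is true of a flag derived from a code. That is so, but it says nothing about whether the vaccine is known, and a reader may take it as assurance that attribution is complete.

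Three stronger readings are tempting, and the documents do not support them.

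- A reader might infer that the incidence is meant to separate vaccine events from NT 201 events. No readable text says so, and NT 201 causality is rated on its own.
- A reader might infer that symptoms suggestive of toxin spread go unattributed. The AESI list is redacted, and AESIs and NT 201 causality are captured whatever this flag says.
- A reader might infer a sizeable undercount. That needs assumed rates of vaccination, reaction and symptom-level reporting, none of which the documents give, and it would cover only the missed events.

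**Conclusion.** The concern holds as a mismatch between a definition and its label. The planned incidence of COVID-19-vaccination-related TEAEs can include reactions to other vaccines and can miss COVID-19 vaccine reactions coded as symptoms. The direction and size of the net error cannot be derived from the documents.

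The conclusion rests on two assumptions: that no coding convention in redacted or unseen text closes the gap, and that the single preferred term is the only route into the category, as the readable text implies. The consequence is confined to one descriptive safety output. It gives no ground to doubt the efficacy analyses, type I error control, power, the NT 201 causality ratings, AESI reporting or the secondary safety endpoints. It is a modest point, worth correcting because correction is cheap.

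**What to change.** Replace the rule in SAP 6.2. Before unblinding, classify a TEAE as related to COVID-19 vaccination if either holds:

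- its verbatim term attributes it to a COVID-19 vaccine, whatever its preferred term; or
- it is coded *Immunisation reaction* and the verbatim term or the concomitant medication record identifies a COVID-19 vaccine.

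Report *Immunisation reaction* events with no identifiable vaccine in a separate row. SAP 6.2 currently ignores TEAEs with a missing relationship when these incidences are calculated, so without that row they would drop out of sight. Revise the sentence on missingness to match. If a coding convention already exists, cite it.

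First check that the vaccine records are adequate. The drug-name and date detail in Protocol 8.3 is set out for medication taken before enrolment, on-study therapy changes are to be documented, and vaccines are not mentioned in the readable text. If the records fall short, keep the present count, label it *Immunisation reaction (PT)*, and do not call it COVID-19-vaccination related.

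The cost is a change of SAP wording and one blinded medical review listing, which could be handled at the blinded data review meeting already planned for the per-protocol set. Relabelling alone costs only the wording.
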